11.1 Data Quality Assurance

- All patient data relating to the trial will be recorded on electronic CRFs unless transmitted
 to the sponsor or designee electronically (e.g., laboratory data). The investigator is
 responsible for verifying that data entries are accurate and correct by physically or
 electronically signing the CRF.
- Guidance on completion of CRFs will be provided.
- The investigator must permit trial-related monitoring, audits, IEC review, and regulatory agency inspections and provide direct access to source documents.
- Monitoring details describing strategy, including definition of trial critical data items and
 processes (e.g., risk-based initiatives in operations and quality such as risk management
 and mitigation strategies and analytical risk-based monitoring), methods, responsibilities,
 and requirements, including handling of noncompliance issues and monitoring techniques
 (central, remote, or on-site monitoring) are provided in the monitoring plan.
- The sponsor or designee is responsible for the data management of this trial, including quality checking of the data.
- The sponsor assumes accountability for actions delegated to other individuals (e.g., CROs).
- Records and documents, including signed ICFs, pertaining to the conduct of this trial must be retained by the investigator for 25 years after trial completion unless local regulations or institutional policies require a longer retention period. No records may be destroyed during the retention period without the written approval of the sponsor. No records may be transferred to another location or party without written notification to the sponsor.

11.2 Source Documents

- Source documents provide evidence for the existence of the patient and substantiate the integrity of the data collected. Source documents are filed at the investigator's site.
- Data entered in the eCRF that are transcribed from source documents must be consistent
 with the source documents or the discrepancies must be explained. The investigator may
 need to request previous medical records or transfer records, depending on the trial. Also,
 current medical records must be available.
- Definition of what constitutes source data and its origin can be found in the monitoring plan.
- The investigator must maintain accurate documentation (source data) that supports the information entered in the CRF.
- The sponsor or designee will perform monitoring to confirm that data entered into the CRF by authorized site personnel are accurate, complete, and verifiable from source

Clinical Study: ES2B-C001-S01 EU CT No.: 2024-516333-12-00

documents; that the safety and rights of patients are being protected; and that the trial is being conducted in accordance with the currently approved protocol and any other trial agreements, ICH GCP, and all applicable regulatory requirements.

11.3 Trial and Site Start and Closure

11.3.1 First Act of Recruitment

The trial start date is the date on which the clinical trial will be open for recruitment of patients. The first act of recruitment is the first site open and will be the trial start date.

11.3.2 Trial/Site Closure and Termination

The sponsor or designee reserves the right to close the trial site or terminate the trial at any time for any reason at the sole discretion of the sponsor. Trial sites will be closed upon trial completion. A trial site is considered closed when all required documents and trial supplies have been collected and a trial-site closure visit has been performed.

The investigator may initiate trial-site closure at any time, provided there is reasonable cause and sufficient notice is given in advance of the intended termination.

Reasons for the early closure of a trial site by the sponsor or investigator may include but are not limited to:

For trial termination:

Discontinuation of further trial intervention development

For site termination:

- Failure of the investigator to comply with the protocol, the requirements of the IEC or local health authorities, the sponsor's procedures, or GCP guidelines.
- Inadequate or no recruitment (evaluated after a reasonable amount of time) of patients by the investigator.
- Total number of patients included earlier than expected.

If the trial is prematurely terminated or suspended, the sponsor shall promptly inform the investigators, the IECs, the regulatory authorities, and any CRO(s) used in the trial of the reason for termination or suspension, as specified by the applicable regulatory requirements. The investigator shall promptly inform the patient and should assure appropriate patient therapy and/or follow-up.

11.4 Publication Policy

 The results of this trial may be published or presented at scientific meetings. If this is foreseen, the investigator agrees to submit all manuscripts or abstracts to the sponsor before submission. This allows the sponsor to protect proprietary information and to provide comments.

Clinical Study: ES2B-C001-S01 EU CT No.: 2024-516333-12-00

- The sponsor will comply with the requirements for publication of trial results. In accordance
 with standard editorial and ethical practice, the sponsor will generally support publication
 of multicenter studies only in their entirety and not as individual site data. In this case, a
 coordinating investigator will be designated by mutual agreement.
- Authorship will be determined by mutual agreement and in line with International Committee of Medical Journal Editors authorship requirements.

Clinical Study: ES2B-C001-S01 EU CT No.: 2024-516333-12-00

12 Appendix 1: AEs and SAEs: Definitions and Procedures for Recording, Evaluating, Follow-up, and Reporting

12.1 Definition of AE

AE Definition

- An AE is any untoward medical occurrence in a clinical trial patient, temporally associated with the use of trial intervention, whether or not considered related to the trial intervention.
- NOTE: An AE can therefore be any unfavorable and unintended sign (including an abnormal laboratory finding), symptom, or disease (new or exacerbated) temporally associated with the use of trial intervention.

Definition of Unsolicited AE

- An unsolicited AE is an AE that was not found using specific questions and that is communicated by a patient who has signed the informed consent. Unsolicited AEs include serious and nonserious AEs.
- Potential unsolicited AEs may be medically significant (i.e., symptoms or illnesses requiring
 a hospitalization, emergency room visit, or visit to/by a healthcare provider). The patients
 will be instructed to contact the site as soon as possible to report medically attended
 event(s), as well as any events that, though not medically attended, are of patient's
 concern. Detailed information about reported unsolicited AEs will be collected by qualified
 site personnel and documented in the patient's records.
- Unsolicited AEs that are not medically significant nor perceived as a concern by the patient will be collected during an interview with the patient and by review of available medical records at the next visit.

Events Meeting the AE Definition

- Any abnormal laboratory test results (hematology, clinical chemistry, or urinalysis) or other safety assessments (e.g., ECG, radiological scans, vital signs measurements), including those that worsen from baseline, considered clinically significant in the medical and scientific judgment of the investigator (i.e., not related to progression of underlying disease, or more severe than expected for the patient's condition).
- Exacerbation of a chronic or intermittent pre-existing condition including either an increase in frequency and/or severity of the condition.
- New condition detected or diagnosed after trial intervention administration even though it
 may have been present before the start of the trial.
- Signs, symptoms, or the clinical sequelae of a suspected drug-drug interaction.
- Signs, symptoms, or the clinical sequelae of a suspected overdose of either trial intervention or a concomitant medication. Overdose per se will not be reported as an AE/SAE unless it is an intentional overdose taken with possible suicidal/self-harming intent. Such overdoses should be reported regardless of sequelae.

Clinical Study: ES2B-C001-S01 EU CT No.: 2024-516333-12-00

Events not Meeting the AE Definition

- Any abnormal laboratory findings or other abnormal safety assessments that are associated with the underlying disease, unless judged by the investigator to be more severe than expected for the patient's condition.
- The disease/disorder being studied or expected progression, signs, or symptoms of the disease/disorder being studied, unless more severe than expected for the patient's condition.
- Medical or surgical procedure (e.g., endoscopy, appendectomy): the condition that leads to the procedure is the AE.
- Situations in which an untoward medical occurrence did not occur (social and/or convenience admission to a hospital).
- Anticipated day-to-day fluctuations of pre-existing disease(s) or condition(s) present or detected at the start of the trial that do not worsen.

12.2 Definition of SAE

An SAE is defined as any untoward medical occurrence that, at any dose, meets one or more of the criteria listed:

a) Results in death

b) Is life threatening

The term *life threatening* in the definition of *serious* refers to an event in which the patient was at risk of death at the time of the event. It does not refer to an event, which hypothetically might have caused death, if it were more severe.

c) Requires inpatient hospitalization or prolongation of existing hospitalization

- In general, hospitalization signifies that the patient has been admitted (usually involving at least an overnight stay) at the hospital or emergency ward for observation and/or treatment that would not have been appropriate in the physician's office or outpatient setting. Complications that occur during hospitalization are AEs. If a complication prolongs hospitalization or fulfills any other serious criteria, the event is serious. When in doubt as to whether hospitalization occurred or was necessary, the AE should be considered serious.
- Hospitalization for elective treatment of a pre-existing condition that did not worsen from baseline is not considered an AE.

d) Results in persistent or significant disability/incapacity

- The term disability means a substantial disruption of a person's ability to conduct normal life functions.
- This definition is not intended to include experiences of relatively minor medical significance such as uncomplicated headache, nausea, vomiting, diarrhea, influenza, and accidental

Clinical Study: ES2B-C001-S01 EU CT No.: 2024-516333-12-00

trauma (e.g., sprained ankle) that may interfere with or prevent everyday life functions but do not constitute a substantial disruption.

e) Is a congenital anomaly/birth defect

f) Other important medical events

- Medical or scientific judgment should be exercised by the investigator in deciding whether SAE reporting is appropriate in other situations such as important medical events that that may not be immediately life-threatening or result in death or hospitalization but may jeopardize the patient or may require medical or surgical intervention to prevent one of the other outcomes listed in the above definition. These events should usually be considered serious.
- Examples of such events include invasive or malignant cancers, intensive treatment in an emergency room or at home for allergic bronchospasm, blood dyscrasias, convulsions not resulting in hospitalization, or development of intervention dependency or intervention abuse.

12.3 Adverse Event of Special Interest (AESI)

An AESI is a pre-specified medically significant event that has the potential to be causally associated with a vaccine product that needs to be carefully monitored and confirmed by further special studies. In this study the following events are considered AESIs:

- DLT
- CTRCD
- · Immune system disorder

Assessment of Severity

The PI will assess all AEs for severity in accordance with the following standard ratings. The severity of each AE (i.e., non-serious and SAEs) is to be assessed by the Investigator using the National Cancer Institute (NCI) Common Terminology Criteria for Adverse Events (CTCAE, Version 5.0) as indicated in Table 15. When changes in the severity of an AE occur more frequently than once a day, the maximum severity for the event should be noted for that day. Any change in severity of signs and symptoms over a number of days will be captured by recording a new AE, with the amended severity grade, and the date (and time, if known) of the change.

Clinical Study: ES2B-C001-S01 EU CT No.: 2024-516333-12-00

Table 15: National Cancer Institute (NCI) Common Terminology Criteria for Adverse Events (CTCAE) reporting (V5.0).

Grade	CTCAE
Grade 1	An AE that is asymptomatic; or involves mild or minor symptoms; or is of marginal clinical relevance; or consists of clinical or diagnostic observations alone; or for which intervention is not indicated; or for which only non-prescription intervention is indicated.
Grade 2	An AE for which only minimal, local, or non-invasive intervention (e.g., packing, cautery) is indicated; or that limits instrumental activities of daily living (e.g., shopping, laundry, transportation or ability to conduct finances).
Grade 3	An AE that is medically significant but not life-threatening; or for which inpatient care or prolongation of hospitalization are indicated; or that is an important medical event that does not result in hospitalization, but may jeopardize the subject or may require intervention either to prevent hospitalization, to prevent the AE from becoming life-threatening or causing death; or that is disabling; or that results in persistent or significant disability, incapacity, or limitation of self-care activities of daily living (e.g., getting in and out of bed, dressing, eating, getting around inside, bathing, or using the toilet).
Grade 4	An AE that has life-threatening consequences; for which urgent intervention is indicated; that puts the subject at risk of death at the time of the event if immediate intervention is not undertaken; or that causes blindness or deafness.
Grade 5	The termination of life as a result of an AE.

Assessment of Causality

- The PI will assess the causality/relationship between the study drug and the AE based on medical judgment and considering the definitions of the "Assessment of Relationship of Adverse Events to Investigational Medicinal Product" described in Table 16, and all contributing factors. The investigator is obligated to assess the relationship between trial intervention and each occurrence of each AE/SAE.
- For causality assessment, the investigator will also consult the IB for ES2B-C001 and/or
 [adjuvant] . The investigator may change their opinion of causality in light of
 follow-up information and send an SAE follow-up report with the updated causality
 assessment.
- The causality assessment is one of the criteria used when determining regulatory reporting requirements.

Clinical Study: ES2B-C001-S01 EU CT No.: 2024-516333-12-00

Table 16: Assessment of relationship of Adverse Events (AEs) to investigational medicinal product (IMP).

	Assessment of Relationship of Adverse Events to IMP
Definitely Related	A clinical event, including laboratory test abnormality, occurs in a plausible time relationship to treatment administration, and which concurrent disease or other drugs or chemicals cannot explain. The response to withdrawal of the treatment (dechallenge*) should be clinically plausible. The event must be definitive pharmacologically or phenomenologically, using a satisfactory rechallenge† procedure if necessary.
Probably Related	A clinical event, including laboratory test abnormality, with a reasonable time sequence to administration of the treatment, unlikely to be attributed to concurrent disease or other drugs or chemicals, and which follows a clinically reasonable response on withdrawal (de-challenge). Rechallenge information is not required to fulfill this definition.
Possibly Related	A clinical event, including laboratory test abnormality, with a reasonable time sequence to administration of the treatment, but which could also be explained by concurrent disease or other drugs or chemicals. Information on treatment withdrawal may be lacking or unclear.
Unlikely To Be Related	A clinical event, including laboratory test abnormality, with a temporal relationship to treatment administration which makes a causal relationship improbable, and in which other drugs, chemicals or underlying disease provide plausible explanations.
Unrelated	A clinical event, including laboratory test abnormality, with little or no temporal relationship with treatment administration. May have negative de-challenge and rechallenge information. Typically explained by extraneous factors (e.g., concomitant disease, environmental factors or other drugs or chemicals).

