4.3.2 Definition of Dose-limiting Toxicity (DLT)

A DLT is defined as any grade \geq 3 AE according to the NCI-CTCAE v. 5.0 observed at any time from the first administration of ES2B-C001 (alone or adjuvanted) to the 8 weeks thereafter, which despite standard supportive care and in the opinion of the Investigator, is possibly, probably, or definitely related to adjuvanted or non-adjuvanted ES2B-C001, or other event as described below. Investigators evaluation of relatedness to trial treatment administration should take concomitant medication into account.

DLTs will include:

- 1. Any grade ≥ 3 adverse events except:
 - a. Grade ≥ 3 nausea, vomiting, or diarrhea lasting ≤ 72hours with optimal medical therapy Grade 3 fatigue or anorexia lasting < 7 days.
 - b. Fever that occurs within 48 hours of IMP administration and resolves to Grade 2 within 48 hours and is fully resolved within 7 days.
 - c. Non-clinically relevant isolated biochemical abnormalities (e.g., isolated increase in gamma-glutamyltransferase [GGT]).
 - d. Laboratory values out of normal range without related clinical symptoms, clinically transient isolated in nature.
 - e. Laboratory abnormality that is asymptomatic and deemed by the Investigator not to be clinically significant.
- 2. Grade 3 autoimmune reactions, except Grade 3 autoimmune thyroiditis or other endocrine abnormality that can be managed by endocrine therapy.
- 3. Intolerable or > grade 3 injection-site reactions according to FDA guidance 2007 (table 16 appendix 2).
- 4. Grade 2 decrease in left ventricular ejection fraction (LVEF).
- 5. Treatment delay of >14 days due to any related adverse event(s).

In any case, the reported toxicity should be discussed between the Investigators and both the DSMB and the Sponsor. All toxicities will be graded using NCI-CTCAE Version 5.0 based on investigator assessment.

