9.3.1 Primary endpoint analysis

Total number and incidence of dose limiting toxicities (DLTs), number of patients with DTLs and percentage of patients with DLTs in each dose level and patient population will be reported.

Additionally, the number of DLTs, affected patients and percentage of affected patients will also be reported by preferred term and severity according to CTCAE v5.0 in each dose level and patient population.

The maximum tolerated dose will be determined for each patient population separately as lowest dose level at which ≥33% of patients have record of DLT.

The primary endpoint will be evaluated on the Safety Set.

Clinical Study: ES2B-C001-S01 EU CT No.: 2024-516333-12-00

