9.3.4.1 Adverse events

All recorded adverse events (AEs) will be summarized descriptively by preferred term and system organ class. Total number of AEs, total number of subjects with AE and percentage will be reported by dose level and patient population.

Additionally, AEs will be summarized by seriousness, severity (according to CTCAE v5.0), relationship to treatment and outcome.

9.3.4.2 Physical examination, Vital signs, ECOG, Cardiac evaluations, Clinical laboratory tests Safety variables will be analyzed descriptively according to general rules defined at the beginning of this section by study visit and patient population.

Clinical Study: ES2B-C001-S01 EU CT No.: 2024-516333-12-00

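### Each day-to-day change in grade is recorded as a new AE, so the planned totals of AEs and DLTs, read as written, count grade-change records and not episodes

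*Protocol*

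**What the plan says.** **Recording.** Protocol 12.3, Assessment of Severity, has two rules. For changes within a day, "the maximum severity for the event should be noted for that day". For changes across days, "Any change in severity of signs and symptoms over a number of days will be captured by recording a new AE", carrying the amended grade and the date of change.

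**AE reporting.** Section 9.3.4.1 plans: "Total number of AEs, total number of subjects with AE and percentage will be reported by dose level and patient population". It also splits AEs by seriousness, severity, relationship and outcome.

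**DLT reporting.** Section 9.3.1 plans: "Total number and incidence of dose limiting toxicities (DLTs), number of patients with DTLs and percentage of patients with DLTs in each dose level". It adds that "the number of DLTs, affected patients and percentage of affected patients will also be reported by preferred term and severity".

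**Status.** DLTs and the incidence, nature and severity of AEs and of injection site reactions are primary endpoints (Section 3, Table 3).

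**DLT exceptions with a time limit.** Section 4.3.2 exempts grade 3 or higher "nausea, vomiting, or diarrhea lasting ≤ 72hours with optimal medical therapy", grade 3 fatigue or anorexia of under 7 days, and fever that meets two resolution limits.

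**The concern.** The recording rule makes the AE record a stretch of days at one grade. The analysis sections use the same word, AE, for what they total. Nothing in the protocol says which records belong to one episode, or that the totals are of episodes. A reaction that worsens and then subsides therefore adds several events and enters several severity rows, while an equally severe reaction that stays at one grade adds a single event.

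This bears on the events that the trial expects. Section 2.3 reports persistent induration and oedema with the adjuvanted product in animals, and the protocol calls the adjuvant reactogenic. Appendix 2 grades erythema and induration largely by diameter, so a reaction that grows and shrinks changes grade as it does so. Event totals by dose level would then partly measure how much grades fluctuate. The severity table would also fill up with the lower-grade phases of reactions already counted at their peak.

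**Working it through.** The protocol gives no figure for this point, so there is nothing to reproduce. The check applies its rules to assumed courses by direct counting.

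**Inputs.** One grade per day (the daily maximum, 12.3). A new record opens whenever the grade differs from the day before (12.3). Each course is one episode in one patient. The courses are illustrations, not data.

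**Counting.** Records = 1 + number of day-to-day grade changes.

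| Daily grades | AE records | Records at grade 3 or higher | Patients | Linked episodes (maximum grade) |
|---|---|---|---|---|
| 1-2-3-2-1 | 1 + 4 = 5 | 1 | 1 | 1 (grade 3) |
| 2-2-3-3-2-2-1 | 1 + 3 = 4 | 1 | 1 | 1 (grade 3) |
| 3-3-4-4-3-3 | 1 + 2 = 3 | 3 | 1 | 1 (grade 4) |
| 3-3-2-3-3 | 1 + 2 = 3 | 2 | 1 | 1 (grade 3) |

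**AE totals.** Each illustrated episode gives 3 to 5 AEs. The first course puts two records in the grade 1 row, two in the grade 2 row and one in the grade 3 row.

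**DLT totals.** These multiply only if more than one record of an episode itself meets a DLT criterion. That can happen when the episode moves between grades 3 and 4 (third course) or returns to grade 3 (fourth course). A step down from grade 3 to grade 2 normally adds an AE but no DLT (first two courses).

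**Patient counts.** One affected patient per course under either way of counting.

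**Upper illustration of size.** Assume an evolving reaction after every dose and five doses per patient (8.3.5.2 mentions a fifth dose). At the maximum of 27 patients (9.1) there are 27 × 5 = 135 episodes, which appear as 135 × 3 = 405 or 135 × 5 = 675 AEs. At the planned 9 patients there are 9 × 5 = 45 episodes, appearing as 135 or 225 AEs. The multiplier of 3 to 5 comes from the assumed courses. This is a worst case, not a forecast.

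**Duration.** Take 3-3-4-4-3-3 as a gastrointestinal toxicity. Each record lasts 2 days (48 h), while the unbroken time at grade 3 or higher is 6 days (144 h). Against the 72-hour limit in 4.3.2, the record and the episode fall on opposite sides. In the other three courses the longest single record at grade 3 or higher is as long as the longest unbroken run (1, 2 and 2 days), so the two readings agree unless separate runs are added together.

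**The case against.** **Patient-level results stand beside every total.** Sections 9.3.1 and 9.3.4.1 report affected patients and percentages, which are not inflated. Escalation (4.3.1), the enrollment halt (7.5) and the MTD (9.3.1) all count patients. This stands in full: the multiple counting by itself changes no dose decision.

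**Collapsing records is routine SAP work.** The SAP, the safety management plan (12.4) and the CRF completion guidance (11.1) are not shown, and any of them may link the records. This stands in part. The absence of a tabulation rule is not the point. The protocol states a recording rule and states totals, and together they define a count of records. The SAP need only be final before database lock (Section 9), whereas the link between records is best collected as events are entered.

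**DLT totals are less exposed than AE totals.** This stands, as the working shows.

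**A stronger reading about DLT timing.** A reader might infer that the timed exceptions restart at each grade change, so that a real DLT is missed. The documents do not say so. Section 4.3.2 ties each limit to the toxicity and not to an AE record. The gastrointestinal exception covers grade 3 or higher, so it spans grades 3 and 4 by its own terms. The fever exception follows one fever down through the grades. The fatigue and anorexia limit is tied to grade 3, so a step down ends that period under either recording rule. Investigators, DSMB and sponsor discuss reported toxicities (4.3.2), and the DSMB checks reported DLTs against the criteria (10.7). Dated grade changes also allow time at grade 3 or higher to be reconstructed. What remains is that the recording rule and the duration limits use different units and the protocol does not say how they fit together.

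**Conclusion.** The point holds as a minor one about reporting. With the recording rule in 12.3 and no stated link, the totals and severity splits in 9.3.1 and 9.3.4.1 are counts of grade-change records. In the illustrated courses one episode becomes 3 to 5 AEs, and an episode that crosses between grades 3 and 4 or returns to grade 3 can contribute more than one DLT to the total. How far real totals would rise depends on how often reactions change grade from day to day, for which the protocol gives no figure.

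The conclusion assumes that injection site reactions follow the same recording rule as other AEs and that no unseen document already collapses the records. It does not extend to patient-level incidence, to dose escalation or to the MTD. On the DLT exceptions it supports only a request for reconciliation between 12.3 and 4.3.2.

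**What to change.** 1. Keep the grade-change records, since they preserve the course of each reaction, and add an eCRF field that links the records of one episode.
2. State in 9.3.1 and 9.3.4.1 that event totals and severity tables count each linked episode once, at its maximum grade. Patient counts and percentages stay as planned.
3. Separately, reconcile the recording rule in 12.3 with the duration-based exceptions in 4.3.2, so that it is clear how the duration of an episode recorded as several AEs is read. The reading is for the sponsor to settle; no clinical rule is proposed here.

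The cost is one eCRF field, one programming step and a short clarification in the text. Sample size, visits and data already planned are unchanged.
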